8.0 Patient Disposition

[figure not shown]
Subject accountability overall and by current investigator will be summarized with number and percentage of subjects for the ITT, ITT-E, mITT, mITT-E, RR and safety population by treatment groups defined in Section 5.1.

For subjects in RR population, the following additional cohorts will be summarized by number and percentage

- Subjects with re-induction dose
- Subjects without re-induction dose
- Subjects who switched to open-label 0.6 mg/kg ew
- Subjects who switched to open-label 40 mg ew
- Subjects with dose de-escalation vs. de-escalation/re-escalation

Subject final status including the following categories will be summarized by number and percentage:

- Subjects who completed the study (Week 52) [for the mITT, mITT-E, RR and safety population]
 - on double-blind maintenance treatment without re randomization due to disease flare

- on double-blind maintenance treatment after re randomization due to 1st disease flare
- on OL maintenance treatment after re randomization due to 2^{nd} ($\pm 3^{rd}$) disease flare
- Subjects who discontinued while receiving induction treatment [for the ITT, ITT-E and safety population]
- Subjects who discontinued while receiving maintenance treatment [for the mITT, mITT-E, RR and safety population]
 - on double-blind maintenance treatment without re randomization due to disease flare
 - on double-blind maintenance treatment after re randomization due to 1st disease flare
 - o nOL maintenance treatment after re randomization due to 2^{nd} ($\pm 3^{rd}$) disease flare

In addition, for the ITT, ITT-E, mITT, mITT-E, RR and safety population defined in Section 5.1, the reasons for premature discontinuation of study drug (primary reason and all reasons) will be summarized with frequencies and percentages. Subjects may have multiple reasons for prematurely discontinuing study drug, but will be counted only once for the primary reason.

9.0 Study Drug Exposure and Compliance

A summary of analyses and study populations for study drug exposure is provided in Table 5

[figure not shown]

Table 5. Summary of Study Populations for Exposure and Compliance

Study Drug Exposure and				
Compliance	ITT(-E)	mITT(-E)	RR	Safety
Induction-Exposure	X			X
Maintenance-Exposure		X	X	X^{a}
ADA exposure after disease flare			X	
Overall ADA exposure during study			X	X
Treatment Compliance				X

a. Restricted to subjects who received at least one dose of the study drug during maintenance phase.

The duration (days) of study drug exposure and treatment compliance (%) will be summarized using descriptive statistics by treatment group. Moreover, the patient-years of study drug exposure will be provided.

Details for calculating study drug exposure duration are provided below (Section 9.1).

[figure not shown]
Treatment compliance (%) is defined as the number of study drug injections received divided by the number of injections planned. The number injections planned will be derived from the individual patient's course through this study and the corresponding dosing schedule planned for the specific course (see Figure 1, Figure 2, Figure 3, and Figure 4).

9.1 Study Drug Exposure

Induction study drug exposure will be summarized for ITT, ITT-E and safety population by treatment groups defined in Section 5.1. The study drug exposure during induction period does not include the dose received at Week 8. The duration of exposure during induction period will be calculated as follows:

Duration of induction-exposure = last induction dose date - first induction dose date + (max.*) 14 days

*cutting before first dose of study drug in the maintenance period.

Maintenance study drug exposure will be summarized for mITT, mITT-E, RR and safety population (restricted to subjects who received at least one dose of the study drug during maintenance phase). Of note, patients in this study don't receive study drug at Week 52, unless they roll over into Study M10-870, then this will be their first dose of study drug in Study M10-870 (and will be documented in Study M10-870, not Study M11-290). The duration of exposure during maintenance will be calculated as follows:

Duration of maintenance-exposure = last maintenance dose date (prior to potential re-randomization due to 1st disease flare) – first maintenance dose date + (max.*) 14 days

*cutting before first dose of study drug after re-randomization due to 1st disease flare, if applicable, or the first dose of study drug in Study M10-870, if applicable.

[figure not shown]
ADA exposure after re-randomization due to 1st disease flare for the RR population will be calculated as follows:

Duration of ADA exposure after 1st disease flare = last adalimumab dose date in the study after re-randomization due to 1st disease flare – first dose date of adalimumab after re-randomization due to 1st disease flare + (max.*) 14 days

*cutting before first dose of study drug in Study M10-870, if applicable

The overall adalimumab exposure (regardless of double-blind or open-label treatment or if it was rescue therapy after disease flare) will be summarized for the safety population. The duration of overall exposure will be calculated as follows:

- Subjects who are randomized to placebo at Week 8 and who have not been re-randomized due to a disease flare:
 - Overall ADA exposure = Duration of induction-exposure
- Subjects who are randomized to placebo at Week 8 and are re-randomized due to at least one disease flare during maintenance:

Overall ADA exposure = Duration of induction-exposure + (last adalimumab dose date in the study after re-randomization due to 1st disease flare – first dose date of adalimumab after re-randomization due to 1st disease flare + (max.*) 14 days)

*cutting before first dose of study drug in Study M10-870, if applicable

• Subjects who are not randomized to placebo:

Overall ADA exposure = last adalimumab dose date in the study – first dose of adalimumab + (max.*) 14 days.

*cutting before first dose of study drug in Study M10-870, if applicable

[figure not shown]
10.0 Efficacy Analysis

10.1 General Considerations

Efficacy analyses will be performed on the ITT population for the Week 8 efficacy endpoints and on the mITT population for the Week 52 efficacy endpoints, unless otherwise noted. Confirmatory analyses will be restricted to ITT-E and mITT-E.

Endpoints that are of the binary type will be analyzed as proportions by treatment group (as defined in Section 5.1) including 95% CIs. NRI (see Section 6.0) will be used, unless otherwise noted. Endpoints that are of the continuous type will be analyzed as changes from baseline, and reported by treatment group (as defined in Section 5.1) including 95% CIs. LOCF (see Section 6.0) will be used, unless otherwise noted.

[figure not shown]
Confirmatory testing of the co-primary and ranked secondary endpoints will be done on the ITT-E (for Week 8 efficacy endpoints) and mITT-E population (for Week 52 efficacy endpoints), where adalimumab dose groups will be tested against external placebo (see Section 10.2) in a sequentially rejective multiple test procedure in order to ensure that the familywise Type I error (multiple significance level) of 5% is controlled in a strong sense, using one-sample two-sided Chi-square tests. The below graph describes the structure of the multiple test procedure that starts with testing the co-primary endpoints for the

[figure not shown]
combined high and standard adalimumab dose groups versus external placebo and then testing individual dose groups versus external placebo separately, as in the figure below.

The results from the test procedure will be displayed also graphically using R.

Multiple Test Procedure for the Co-Primary and Ranked Secondary Endpoints

Assuming ε = 0.0005; C = testing the endpoint for the combined high and standard adalimumab dose groups against external placebo; HD = testing the endpoint for the high adalimumab dose against external placebo; SD = testing the endpoint for the standard adalimumab dose against external placebo; P_1 = co-primary induction endpoint; P_2 = co-primary maintenance endpoint; P_3 = ranked secondary endpoint i (i = 1,...,4)

[figure not shown]

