The pharmacological treatment of UC in childhood is largely the same as in adulthood. Conventional pharmaceutical therapies do not completely abate the inflammatory process and have significant side effects. Conventional therapies for the induction of remission have included anti-inflammatory agents (5-aminosalicylic acid [5-ASA] derivatives and corticosteroids) and the immunomodulatory agent cyclosporine. 5-ASA derivatives as well as immunomodulatory agents (azathioprine or 6-mercaptopurine [6-MP]) have been used for the maintenance of remission.¹³ Corticosteroids are not effective for the maintenance of remission. In addition to the induction and maintenance of clinical remission, absence of adverse effects on linear growth and maturation is demanded from therapy of pediatric UC. Similar to adults, corticosteroid dependence is frequent, but long-term corticosteroids are absolutely contraindicated because they do not maintain remission and have a negative effect on linear growth and bone mineralization.² Infliximab (a chimeric monoclonal anti-tumor necrosis factor [TNF]- α antibody) was approved in Europe for the treatment of pediatric patients with severe UC and in the US for the treatment of pediatric patients with moderate to severe UC based on the results of a recent study.¹⁴

The safety and efficacy of adalimumab for the induction and maintenance of clinical remission in adult subjects with moderately to severely active UC has been studied in two completed double-blind clinical trials (Study M06-826 and Study M06-827) and a completed open-label study (Study M10-223).¹⁵⁻¹⁸ In addition, adalimumab has shown clinically relevant improvements in IBDQ scores compared to placebo for up to 52 weeks in these subjects.¹⁹

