An x-ray of the wrist for the assessment of bone age will be obtained at Screening and at Week 52/Premature Discontinuation visit to determine changes in bone maturation. Sites should use the Greulich and Pyle method for reading the x-ray.²⁰ The x-ray report requires the signature of the radiologist who read the films or of the investigator. The bone age that is determined by the x-ray should be recorded on the eCRF. Assessment of bone age will not be required for subjects with the Premature Discontinuation visit at or before Week 26. An x-ray of the wrist for the assessment of bone age at Screening will

not be required if the subject had an x-ray within 90 days of Screening, provided all protocol required documentation is available at the site.

Anthropometric Evaluations

Height and weight obtained at Baseline, Week 26 and Week 52/Premature Discontinuation will be used by AbbVie Data Management and Statistical groups for determination of BMI and "z" score (observed height velocity [cm/yr] – mean height velocity for age and sex [cm/yr]/SD of the mean) for height.

At Baseline, height from 6 months prior to Screening and maximal weight attained within preceding 6 months will be recorded.

Tanner Stage

Tanner Stage will be assessed at Screening (or at Baseline as appropriate), Week 26 and Week 52/Premature Discontinuation Visit if premature discontinuation occurs after Week 26. Tanner Staging should be captured on the appropriate eCRF page.

Pediatric Ulcerative Colitis Activity Index (PUCAI)

A PUCAI score will also be calculated at all study visits beginning at Baseline.

An example of the PUCAI is located in [Appendix C](#).

The PUCAI score will be assessed using subject-reported symptoms and activity level. The answers should reflect symptoms and activity level during the previous 24 hours. The PUCAI scores of the last 2 days prior to each study visit will be averaged and used for the PUCAI scores for each study visit. The total PUCAI score will be rounded up to the next 5-point interval as applicable. In order to account for unavailable or excluded diary entries as per the provisions given below diary entries for the PUCAI score of the most recent 2 days within 10 days prior to each study visit will be used.

Diary entries of the following days should not be included in the 2 days prior to the visit that are evaluated for the PUCAI score: (1) the day the subject received medication for

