Non-responder Imputation (NRI): The NRI approach is used for all binary efficacy variables. These variables can take values of 'Response' (i.e., response, remission or mucosal healing) or 'Non-response' (i.e., non-response, non-remission or no mucosal healing) or may be missing for any reason including discontinuation from study. According to the NRI method all missing values will be considered as 'Non-Response'. Subjects re-randomized due to disease flare will be considered as 'Non-Responders' at and after their 1st re-randomization. The confirmatory efficacy analyses will use NRI approach to impute the missing values.

Additionally, only for sensitivity analyses on the mITT population, a **modified NRI** (**mNRI**) approach to impute the missing values will be used. For mNRI method, subjects re randomized due to disease flare will be considered as 'Non-Responders' at and after the switch to the open-label therapy (2nd disease flare).

Last Observation Carried Forward (LOCF): For categorical and continuous efficacy variables the following rules will be used for LOCF approach:

- Baseline and pre-baseline values will not be used to impute the missing post-baseline values, and
- Missing values after baseline will be imputed using the last non-missing values
 after baseline and prior to the missing value. This includes values from
 unscheduled visits and visits where the measurement was not planned to be
 collected per protocol.
- For subjects who were re-randomized due to disease flare, the last non-missing value before or at the re-randomization after 1st disease flare will be carried forward.

[figure not shown]
Unless otherwise noted, for composite scores which consist of several component subscores, components will be imputed first and the composite score will be calculated based on imputed component subscores. Only if composite score still can't be calculated after imputing component subscores, then the previous composite score will be carried forward. The LOCF analysis will only be performed as sensitivity analysis.

Observed Cases (OC): Observed case analysis will be performed on data until 1st re-randomization of subjects with a disease flare. The following rule will be used: missing values will not be used for the observed case analysis. The OC analysis will only be performed as sensitivity analysis.

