10.4 Secondary Efficacy Analyses

[figure not shown]
The secondary efficacy endpoints are divided into two groups. The first group consists of ranked secondary efficacy endpoints. The second group includes all other secondary efficacy endpoints and special assessments.

The ranked secondary efficacy endpoints in hierarchical order are:

[figure not shown]
- Proportion of subjects in Mayo clinical response at Week 52 in Week 8 responders per PMS;
- Proportion of subjects who achieve mucosal healing at Week 52 as measured by Mayo endoscopy subscore (defined as ≤ 1) in Week 8 responders per PMS;
- Proportion of subjects who achieve Mayo clinical remission at Week 52 in Week 8 remitters per PMS;
- Proportion of subjects receiving systemic corticosteroids (UC related or non-UC related) at Baseline who have discontinued systemic corticosteroids prior to Week 52* and are in Mayo clinical remission at Week 52 in Week 8 responders per PMS.

Additional exploratory secondary analyses will be performed for:

[figure not shown]
- Proportion of subjects in PMS clinical remission at Week 52 in Week 8 responders per PMS;
- Proportion of subjects in PUCAI remission (defined as < 10) at Week 8;
- Proportion of subjects in PUCAI response (defined as a decrease in PUCAI
 ≥ 20 points from Baseline) at Week 8;

- Proportion of subjects in PUCAI remission (defined as < 10) at Week 52 in Week 8 responders per PMS;
- Proportion of subjects in PUCAI response (defined as a decrease in PUCAI
 ≥ 20 points from Baseline) at Week 52 in Week 8 responders per PMS;
- Proportion of subjects receiving systemic corticosteroids at Baseline who discontinue systemic corticosteroids prior to Week 52* and are in PUCAI remission at Week 52 in Week 8 responders per PMS;
- Change from Baseline in total IMPACT III Quality of Life score and subscores over time for subjects at least 9 years old at Baseline;
- Change from Baseline in WPAI scores over time;
- Change from Baseline in "z" scores for height at Week 26 and Week 52;
- Change from Baseline in BMI at Week 26 and Week 52;
- Change from Baseline in "z" scores for weight-for-age at Week 26 and Week 52;
- Proportion of subjects at appropriate Tanner stage (see Section 6.0) at Baseline, Week 26 and Week 52 (OC analysis);
- Proportion of subjects in PMS response over time;
- Proportion of subjects in PMS remission over time;
- Proportion of subjects in PUCAI response over time;
- Proportion of subjects in PUCAI remission over time;

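### Height z, BMI and weight-for-age z are frozen at the first flare re-randomisation in both LOCF and observed-case analyses, so growth z-scores measured afterwards are not reported at Week 26 or Week 52

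*SAP*

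**What the plan says.** SAP 10.1 sets the general rule for continuous endpoints: "LOCF (see Section 6.0) will be used, unless otherwise noted". SAP 10.4 then lists the growth endpoints among the exploratory secondary analyses, for example "Change from Baseline in BMI at Week 26 and Week 52", with the height and weight-for-age z-scores at the same two visits. None carries a note naming another method. Tanner stage, in the same list, is explicitly marked as observed case.

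SAP 6.0 defines LOCF. Baseline may not be carried forward. Values from "unscheduled visits and visits where the measurement was not planned to be" collected may be. For subjects re-randomised because of a flare, the last non-missing "value before or at the re-randomization after 1st disease flare will be carried forward". The observed-case definition in the same section uses data only up to the first re-randomisation. SAP 6.0 also describes LOCF as a sensitivity analysis only, which does not agree with SAP 10.1. Protocol 8.1.4 plans both LOCF and observed case and does not say which leads.

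On measurement, Protocol 5.3.1.1 says: "Height and weight obtained at Baseline, Week 26 and Week 52/Premature Discontinuation will be used" for BMI and the height score. Footnote b to Protocol Table 1 lists weight, but not height, among the vital signs at each visit. Footnote b to SAP Table 1 and SAP 11.4 list height as well as weight at each visit.

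**The concern.** Stopping the clock at rescue is a familiar convention for a disease-activity score. For growth it has a different consequence. Children re-randomised after a flare can remain in the study to Week 52 and be measured there, and from Week 12 a flare permits starting or increasing corticosteroids with Medical Monitor approval. Protocol 3.2 says that "absence of adverse effects on linear growth and maturation is demanded from therapy of pediatric UC" and names long-term corticosteroids as harmful to linear growth. The plan therefore collects growth data in the children most exposed to that risk, then substitutes pre-flare values, or nothing, in the endpoints meant to describe growth. A reader of the Week 52 growth table would not see what happened to these children after the flare.

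**Working it through.** The documents state no figure for the growth endpoints, so there is none to reproduce. The check traces the rules and then measures how old a frozen value can be.

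**1. Which method applies.** The SAP 10.1 default, with no exception in SAP 10.4, gives LOCF. The statement in SAP 6.0 that LOCF is sensitivity-only leaves the main analysis unclear, but the alternative it leaves, observed case, is also cut at the first re-randomisation. Neither route uses a value measured afterwards.

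**2. Whether another output restores those values.** The efficacy summary for the re-randomised population in SAP 10.7 covers only Mayo response and remission. SAP 11.4 covers height, weight and BMI during overall adalimumab exposure, which under SAP 9.1 includes time after rescue. It does so as raw change to minimum, maximum and final value, without z-scores and not at Weeks 26 and 52. Raw height rises in any growing child, so this does not replace an age-adjusted score.

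**3. Age of the frozen value.** Nominal days are from the visit-window table in SAP 6.0, with Week 52 = Day 365. Gap = 365 − d; share = gap / 364.

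| Re-randomised at | d | Gap to Week 52 (days) | Share of follow-up |
|---|---|---|---|
| Week 12 | 85 | 280 | 77% |
| Week 18 | 127 | 238 | 65% |
| Week 26 | 183 | 182 | 50% |
| Week 34 | 239 | 126 | 35% |
| Week 42 | 295 | 70 | 19% |

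These gaps assume a measurement at the re-randomisation visit; otherwise they are longer. For re-randomisation before Week 26 the Week 26 value is also frozen: 183 − 85 = 98 days old from Week 12, and 183 − 127 = 56 days old from Week 18. With measured values the gap would be 0.

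**4. What is available to carry if re-randomised before Week 26.**

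| Endpoint | Protocol schedule | SAP schedule |
|---|---|---|
| Height z, BMI | No post-baseline height; baseline barred; no value | An earlier post-baseline height is carried |
| Weight-for-age z | Weight at each visit; frozen, not absent | Same |

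**5. Scale, on assumptions only.** SAP 10.1 places Week 52 endpoints on the mITT population, planned at 57 adalimumab plus about 12 placebo subjects = 69. If 20% to 50% were re-randomised (assumed), 0.2 × 69 ≈ 14 to 0.5 × 69 ≈ 35 children would be affected; among the 57 on adalimumab, 11 to 29.

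The effect on height z depends on what is carried, which the SAP does not say. If raw height is carried and scored at the Week 52 age, shortfall = v × (365 − d)/365.25. With assumed growth v of 2 to 6 cm/year this is 1.53 to 4.60 cm from Week 12, 1.00 to 2.99 cm from Week 26 and 0.38 to 1.15 cm from Week 42. Dividing by an assumed SD (2 cm/year with SD 8 cm, up to 6 cm/year with SD 6 cm) makes z too low by 0.19 to 0.77, 0.12 to 0.50 and 0.05 to 0.19 respectively. If the z-score itself is carried, there is no mechanical fall; the value is simply out of date.

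**The case against.** The strongest reply is that freezing at rescue is a deliberate and consistent choice. After re-randomisation placebo children receive adalimumab, and children in any arm may later move to open-label weekly dosing. Post-rescue values compared by maintenance arm therefore answer a different question from the effect of the assigned regimen. This stands: it is a reason to show an as-measured analysis by re-randomisation status, with that caveat, and it means the frozen analysis is not simply an error. It is also true that these endpoints are exploratory, and that SAP 11.4 does report some post-flare measurements.

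Three stronger readings are tempting, and the documents do not support them.

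- A reader might infer that any child who flares before Week 26 contributes no follow-up height. That follows only from the protocol schedule, not from the SAP's. It never applies to weight, and the trigger is re-randomisation, which is optional, rather than the flare itself.
- A reader might infer that Week 52 height is understated by a fixed number of centimetres, or that carrying BMI forward assumes a child stops growing. Raw height is not one of the listed endpoints, and an unchanged BMI is compatible with growth.
- A reader might infer that the growth results describe mainly children who did well. Re-randomised children can still contribute pre-flare values, and no flare rate is stated.

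**Conclusion.** The concern holds as a reporting gap. Under the rules as written, height z, BMI and weight-for-age z measured after a first flare re-randomisation enter neither the LOCF nor the observed-case analysis at Week 26 or Week 52, and no other planned output gives the z-scores. The value shown at Week 52 can be 70 to 280 days old for re-randomisation between the Week 42 and Week 12 visits. On the protocol's height schedule, height z and BMI are missing altogether if re-randomisation comes before Week 26.

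This rests on reading the flare rule in SAP 6.0 as replacing later measured values and not only filling gaps. The matching cut-off in the observed-case definition supports that reading. The number of children, and the direction and size of any bias, cannot be determined from the documents; the figures in step 5 of the working are illustrations. No confirmatory test is affected. It is a low-cost improvement to an exploratory but clinically relevant part of a paediatric trial.

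**What to change.** In SAP 10.4, add an analysis of change in height z, BMI and weight-for-age z using all values measured at Week 26 and Week 52, regardless of re-randomisation or rescue and without LOCF. Present it by maintenance arm and re-randomisation status, with a note that re-randomised placebo children received adalimumab. Keep the frozen analysis only as a secondary display, and state there whether the raw measurement or the z-score is carried.

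Reconcile two conflicts at the same time: whether height is taken at each visit (SAP Table 1 and 11.4) or only at Baseline, Week 26 and Week 52/Premature Discontinuation (Protocol 5.3.1.1 and Table 1), and whether LOCF is the default (SAP 10.1) or a sensitivity analysis only (SAP 6.0).

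The cost is SAP wording and one table from data already collected. The drawback is that post-rescue values reflect rescue treatment as well as the assigned arm, which is why re-randomisation status must be shown.
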